#### General study characteristics

• dropout rate

Is the dropout rate consistent with the literature (approximately 15-20% for lifestyle

interventions)? The analysis will be reported separately for the two sub-studies and randomised trial arms.

- *compliance* What is the compliance across the two sub-studies?
- sign-up rate

Out of participants that originally registered interest, how many wanted to finally participate and how many were included after meeting the criteria?

Moreover, the study will describe longitudinal alterations in a variety of health parameters (see also Fig. 2):

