#### 5.4.3 Subsidiary outcomes or objectives

Optional samples are collected at month 12 and month 18 after inclusion into the study. Samples may be collected to evaluate long-term stability of changes in those participants that showed epigenetic and other biological changes in response to the intervention:

- ongoing "compliance" to smoking cessation or intermittent fasting: participants are not specifically instructed to continue with any intervention but it will be evaluated how many participants continue to be smoke-free or undergo intermittent fasting. It is likely that individuals that were highly compliant to begin with may be more likely to return for optional follow ups, which will need to be considered for this analysis.
- variability in epigenetic and other health markers evaluated in primary and secondary endpoints at month 6 and month 12 and/or month 18

Additionally, it is a subsidiary objective to identify changes in the following parameters in response to the intervention in subgroups of participants:

- blood (immune) cell identity and composition as assessed via multiomic single cell RNA- and ATAC-seq in a subgroup of patients (pilot study, baseline and 2 months): reduced numbers of inflammatory cell populations, increased chromatin accessibility at PCGT sites.
- epigenetic reprogramming signatures
- characterisation of epigenetic alterations following intervention in "compliers", and their relation to ageing and exposure signature (scores). Many studies have previously identified signatures that that capture epigenetic ageing yet the biological meaning of them remains unclear. It may be beneficial to identify CpG markers that are changed in response to a putative health-promoting intervention specifically and correlate with clinically meaningful changes (e.g. gut microbiome, lung function) in

a well-characterised longitudinal dataset. We may chose to undertake this subsidiary analysis pending the outcome of initial results.

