#### 6.4.4 Secondary endpoint reporting

To investigate the magnitude and temporal dynamics of changes in methylation indices for each surrogate tissue, namely cervical, buccal, and blood, linear mixed-effects models will be estimated, combining tissues where applicable. The use of random slopes and intercepts will be explored (R package lme4 or nlme, lmer function). Compliance score, sample cell composition, BMI, smoking status, or other factors identified during exploratory data analysis may be used as covariates. Additionally, in a descriptive manner, the change from baseline will be reported within each tissue and paired comparisons will be carried out. Examples of linear models (covariates may be altered or extended) are provided below:

$$model_{intermittent \ fasting} = lmer(score \sim compliance + sample \ type + BMI + ic + age_{baseline} + (time|id), data = data)$$
(1)

$$model_{smoking \ cessation} = glmer(score \sim compliance + sample \ type + smoking \ status + ic + age_{baseline} + (time|id), data = data)$$
(2)

Separate models per sample type may be even more informative, this will be explored during exploratory data analysis.

Using models based on equations in equations 1 and 2, the data will be characterised as follows:

- 1. Estimation of average changes in all participants
- 2. Estimation of changes for individual participants
- 3. Characterisation of degree of heterogeneity across participants (variance across participants, quantified by random effects)
- 4. Identify factors (fixed effects) that predict changes (e.g. compliance score)

Beta estimation will be conducted using maximum likelihood estimation. Following model fitting, residuals will be visualised and qq plots will be generated. If p values are needed for reporting, these will be obtained via Kenward-Roger estimation in the R package lmerTest. A sensitivity analysis will be conducted using either complete case analysis or multiple imputed values

Comparison between sample types may be done via incorporation of data into mixed effects models with an additional covariate (sample type). The sample type with the biggest changes in association with the compliance score may be the most suitable surrogate type for monitoring longitudinal health effects.

Data will be visualised using spaghetti plots, colouring by compliance score and applying facet wraps by sample type.

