# 6.5 Clinical and epidemiological data

#### 6.5.1 Quality control

Clinical data is recorded using an electronic case report form (eCRF) or databases (e.g. fitness tracker). The eCRF data entry includes a plausibility check. Data will be harmonised by the data analyst prior to exploration and missing data, and patterns thereof, will be explored.

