#### 6.5.2 Exploratory analysis

Data normality will be thoroughly visualised and summarised prior to analysis. The data distribution, including distribution of missing data, will be evaluated.

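### The SAP's only missing-data sensitivity analysis, complete case or multiple imputation for the secondary epigenetic models, cannot reveal bias if women who lapse or do not respond lack month 6 samples

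*SAP*

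**What the plan says.** SAP section 6.4.4 plans linear mixed models of the methylation scores over time in cervical, buccal and blood samples. The first listed use is to estimate the average change over all participants. On estimation it says: "Beta estimation will be conducted using maximum likelihood estimation". On missing data it says: "A sensitivity analysis will be conducted using either complete case analysis or multiple imputed values". The choice between the two is left open, and no imputation model or missingness assumption is given.

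On covariates: "Compliance score, sample cell composition, BMI, smoking status, or other factors identified during exploratory data analysis may be used as covariates". The compliance score appears in both example models, with a note that covariates may be altered or extended.

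Elsewhere missing data are only described. Section 6.5.1 says "missing data, and patterns thereof, will be explored" and section 6.5.2 says "The data distribution, including distribution of missing data, will be evaluated". Sections 6.7.1, 6.8.1, 6.9.1 and 6.10.1 plan to visualise missingness. The g methods in section 6 address non-adherence, not absent outcomes.

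The dropout benchmark in section 5.4.2 is "approximately 15-20% for lifestyle" interventions. It is a literature figure for comparison, not a design input.

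**The concern.** A sensitivity analysis is useful if it relaxes the assumption most likely to fail. A likelihood mixed model is valid when missingness depends only on observed data that are in the model. In a lifestyle study the obvious threat is that women who lapse, or see no effect, stop coming. Neither planned check moves in that direction: standard multiple imputation keeps the same assumption, and complete case needs a stronger one.

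The design gives this some weight. There is no control group (sections 3.1 and 5.3), so selective loss feeds straight into the estimated change from baseline, with no comparator to offset it. The target is the average over all participants, which includes those who leave. Close agreement between the model and multiple imputation could then be taken as evidence that dropout did little harm, when that question had not been asked.

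**Working it through.** **1. The plan's own figure.** Section 3.6 gives n = 60, difference 0.2, SD 0.44, alpha 0.05 and power 0.94. Read as a two-sided paired comparison: Φ(0.2 × √60 / 0.44 − 1.96) = Φ(3.521 − 1.96) = Φ(1.561) = 0.941; the exact t version gives 0.934. The stated power is reproduced, so 0.20 and 0.44 serve below as the mean and SD of the change. The two dropout rates are the 15% and 20% of section 5.4.2.

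**2. Assumed scenario.** Stayers change by −0.20, and leavers are at baseline at month 6.
- All-women change at 15%: 0.85 × (−0.20) = −0.17
- All-women change at 20%: 0.80 × (−0.20) = −0.16

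If leavers look like stayers up to their last visit, a missing-at-random analysis that ignores compliance fills in about −0.20 for them and reports −0.20. Relative to the all-women change that is 0.20/0.17 = 1.18 or 0.20/0.16 = 1.25, an overstatement of 18% or 25%.

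**3. Do the planned checks flag informative dropout?** This was simulated with 60 women, visits at months 0, 2, 4 and 6, mean change −0.20 and SD of change about 0.44, with 300 replicates per row. The following are assumptions, not SAP content: random slopes, residual SD 0.205, women leaving after month 2 or month 4, and (except in the completely-at-random rows) log-odds of dropout of 2 per SD of its driver. The likelihood model (ML) had visit means and an unstructured covariance, without the SAP's covariates. MI is standard multiple imputation from earlier visits.

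| Driver of dropout | Rate | Full data | ML | MI | Complete case |
|---|---|---|---|---|---|
| None (completely at random) | 15% | −0.200 | −0.200 | −0.199 | −0.199 |
| None (completely at random) | 20% | −0.204 | −0.204 | −0.204 | −0.204 |
| Observed month 2 change | 15% | −0.196 | −0.195 | −0.195 | −0.245 |
| Observed month 2 change | 20% | −0.194 | −0.194 | −0.193 | −0.262 |
| Woman's true slope | 15% | −0.198 | −0.236 | −0.236 | −0.264 |
| Woman's true slope | 20% | −0.201 | −0.254 | −0.254 | −0.290 |
| Month 6 change itself | 15% | −0.202 | −0.256 | −0.256 | −0.292 |
| Month 6 change itself | 20% | −0.202 | −0.274 | −0.274 | −0.319 |

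In the last four rows dropout is informative.
- MI stays within 0.003 to 0.004 of ML on average in every row, including those where both overstate the reduction by about 0.04 to 0.07.
- Complete case differs from ML by about 0.05 to 0.07 when dropout follows the observed month 2 change, where ML is unbiased. It differs by about 0.03 to 0.045 when dropout is informative, where ML is biased. A gap therefore does not show which situation holds, and complete case errs further in the same direction.

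**4. What a departure from missing-at-random would show.** If the model gives −0.20 and leavers' month 6 change is shifted by δ, the estimate is −0.20 + (dropout rate × δ).

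| Shift δ | 15% dropout | 20% dropout |
|---|---|---|
| 0 | −0.20 | −0.20 |
| +0.2 (no change from baseline) | −0.17 | −0.16 |
| +0.4 | −0.14 | −0.12 |

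Neither analysis named in section 6.4.4, in its standard form, produces this range.

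**The case against.** The strongest reply is that lapsing is measured. Coaches report compliance, with cotinine or ketone cross-checks (section 3.4); visits take place whether or not the woman complies (section 3.11); and non-compliant women are kept and sampled where possible (section 5.3). If some women lapse but stay, their outcomes can inform those of women who lapse and leave. Suppose a further 10% lapse, return to baseline and stay, and lapsing is also known for leavers. At 15% dropout the true change is 0.75 × (−0.20) = −0.15. Ignoring compliance gives (75/85) × (−0.20) = −0.176; imputing with compliance recovers −0.15. At 20% the figures are −0.14, (70/80) × (−0.20) = −0.175, and −0.14.

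This stands as far as it goes, and it is why compliance belongs in the imputation model. But the covariates in section 6.4.4 are optional, the imputation model is unstated, and the score is built from days between visits, so it may be unavailable for a missed month 6 visit. Sampling of non-compliers depends on their being able to continue. Measured compliance also does not capture non-response among women who comply.

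Multiple imputation is also not pointless here. It can handle missing covariates, and auxiliary variables can make missing-at-random more plausible. That is fair, but the SAP commits to neither use.

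Four stronger readings are tempting and not supported:
- That both checks must agree with the mixed model. This is right for standard multiple imputation, but complete case can differ visibly.
- That the SAP itself expects month 6 attendance to depend on compliance. Section 5.4.3 says "individuals that were highly compliant to begin with may be more likely to return for optional follow ups", but this concerns the optional month 12 and 18 visits, and the SAP says it must be considered there. For month 6 it is an analogy only.
- That 18% to 25% is the expected bias. It follows from an assumed mechanism under which return-to-baseline is correct by construction.
- That the primary result is affected. The sentence sits under the secondary models, not the primary paired test, and nowhere does the SAP say it will call results robust to dropout.

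**Conclusion.** The point holds in a limited form. Neither option in the SAP's only missing-data sensitivity analysis departs from missing-at-random towards informative dropout, so neither can reveal the resulting bias. The near-identity of standard multiple imputation and the likelihood model follows from their shared assumption and does not depend on the simulated values. The sizes do: −0.17 or −0.16 against about −0.20 in the return-to-baseline scenario, and an overstatement of about 0.04 to 0.07 under the strong informative dropout simulated. Using measured compliance and sampling non-compliers could remove part of this.

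The study is described as mainly exploratory (sections 2.1 and 3.1) and the sentence covers secondary models with no pass/fail rule. This is a cheap improvement to a stated method, not an error in the primary analysis.

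**What to change.** Replace the sentence in section 6.4.4 with:

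> The mixed model will be checked by multiple imputation that includes compliance score, BMI or smoking status, and earlier visit values. Missing month 6 values will then be (a) centred on the woman's own baseline value and (b) shifted in steps from the missing-at-random value towards no benefit, reporting the estimates and the shift at which the 95% confidence interval for the mean change first includes zero. Complete case results are descriptive only.

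The tipping point is tied to the confidence interval because these models have no formal conclusion to overturn, and section 5.1 already promises 95% intervals. The wording also removes the open choice between two methods.

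The cost is a change of SAP wording and a short extra analysis of data already collected. The downside is a somewhat smaller estimate shown beside the main one.

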# 4 Study population

#### 4.1 Eligibility

#### 4.1.1 Inclusion criteria

- 1. Women aged 30 to 60
- 2. Motivated to change their lifestyle
- 3. Smoking cessation:  $\geq 10$  cigarettes per day for at least the last five years
- 4. Dietary intervention: BMI between 25 and 35
- \* Should 3 and 4 apply, the participant will be allocated to the smoking cessation group.

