# 5.4 Definition of primary, secondary, and subsidiary endpoints

#### 5.4.1 Primary objective

To assess whether a reduction/cessation in risk exposure (smoking, continuous non-timerestricted calorie intake resulting in being overweight/obese) via lifestyle modification over six months results in significant absolute changes in DNA methylation-based disease risk and ageing scores compared to baseline in cervical samples. Scores of the following age signatures will be evaluated:

- signatures that have previously been published, including
  - WID-BC
  - WID-OC
  - WID-EC
  - WID-CIN
  - WID-REA
  - WID-RIA
  - pcgtAge
- signatures that are not yet published but have been developed by the study group
  - Group of markers indicative of (stem) cellular age, e.g. WID-PCGT (general/immune/epithelial),
    WID-SEN (general/immune/epithelial), WID-PRO (general/immune/epithelial),
    etc. thereafter referred to collectively as "WID-SOLA"
- signatures indicative of exposure, e.g.
  - WID-SMK smoking index

Successful completion relates to a significant reduction in two ore more risk scores with no significant in increase in any of the scores.

Analysis will be conducted both ITT, intention to treat, and PP, per protocol, comparing baseline and month 6. ITT analysis may be conducted as a mixed-effects models, using compliance score as a covariate. A per protocol analysis may be conducted either by median compliance rate above or equal to 80%, or alternative split by mean or median compliance rate (see Figure 1).

Subgroup analyses will also be conducted as follows:

- 1. smoking cessation study arm: investigation of the impact of the use of electronic cigarettes on smoking signature scores
- 2. intermittent fasting study arm: investigation of difference between individuals who received ketogenic supplement and those that did not at 6 months
- 3. intermittent fasting study arm: subgroup analysis by fasting pattern (breakfast or dinner skipping)

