# 6 Analysis

Analyses will be conducted and reported separately per sub-study (i.e. smoking cessation and intermittent fasting) after all samples for the month 6 timepoint have been collected. Key analyses will be performed on the ITT population. A per-protocol analysis will be conducted if sufficient individuals are available with above 80% compliance (n=30), or alternatively and additionally a subgroup analyses split by median compliance score (above and beyond, respectively). Descriptive statistics of dynamics over 6 months without an intervention will be reported and if sufficient individuals are present per study arm (n  $\geq 10$ ) that did not adhere, these may be used as a nested control group; although this number is small, it could be informative for dynamic changes without intervention.

The longitudinal manner of data collection enables baseline-controlled pairwise comparison (paired t or Wilcoxon test) for each participant at baseline and after 6 months; linear mixed effects-models may also be employed. Longitudinal dynamics and repeated measurements per participant, evaluating data from baseline, 2, 4, and 6 months, will be assessed using linear (or non-linear) mixed-effects models to account for inter-individual heterogeneity and differences in response (random intercept and slopes, if appropriate). In the intermittent fasting group, cross-sectional analyses may be used to compare effects for use with and without ketogenic supplement. Change from baseline may be reported in a descriptive manner.

Methylation data will be adjusted for sample cell type composition which is known to influence methylation levels. Many of the assessed factors are influenced by age. Dependence on other, non-intervention related covariates will be investigated during the exploratory data visualisation and assessment, and factors may be associated as covariates in mixed-effects models if necessary.

If a number of participants does not adhere to the intervention but continues to provide samples and the assumption of common support holds, we may be able to explore the average treatment effect (ATE) and causal average treatment effect (CATE) using causal inference (g methods) via covariate adjustment for selected secondary outcomes (in particular longitudinal DNA methylation analyses).

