# 6.4 Epigenetic data

#### 6.4.1 Quality control

Samples from the same participant and sample type will be processed as much as possible on the same Illumina Methylation EPIC beadchip (n=8 samples per beadchip), but timepoint position will be randomised on the array to minimise batch effects. DNA methylation data quality control and preprocessing will be performed using a standardised process in the [name] group. The R packages minfi, ChAMP, and ENmix will be used for preprocessing. Briefly, any samples not below a median unmethylated or methylated intensity threshold will be excluded from analysis. Probes that fail the detection p threshold (p <0.01) will be excluded from the dataset. Samples that have more than 10% failed probes will be excluded from the dataset. Beta value distributions will be visualised and outliers identified (for each sample type). Dye bias correction and BMIQ normalisation will be conducted. In addition, control probes will be visualised to check for efficiency of bisulfite conversion, for instance. An amended version of the preprocessing pipeline may be utilised if ongoing experiments demonstrated improvements in reproducibility and noise.

Potential sample mix-ups will be checked by extracting information on control single nucleotide polymorphism (SNP) probes present on the EPIC array. Obvious discrepancies will be further investigated and samples may need to be excluded.

As part of quality control, sample principal components will be checked for association with age, immune cell composition, processing date, beadchip, and other potential biological and technical effects to evaluate batch effects. These will be visualised by correlation heatmaps for the first 10 principal components and principal component and uniform manifold approximation and projection (UMAP) plots. If significant non-biological batch effects are found (e.g. processing day, beadchip), these may be corrected using the ComBat function within the ChAMP R package. As part of quality control, we will also investigate correlation of WID general age with chronological age.

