The abovementioned aspects cover the dynamics of epigenetic indices. Additionally, it will be investigated whether epigenetic indices in certain tissues are associated with other clinical or molecular health-related biomarkers via correlation analysis. No causality can be established for these factors.

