# 7 Systems medicine approach

In addition to the above, we also intend to assess which of the WID scores that dynamically change as a function of protocol adherence are correlating with the change of any of the nonmethylation parameters, for example association of microbiome markers in with epigenetic age (WID-SOLA markers).

Briefly, we aim to conduct three analyses:

- 1. Evaluation of dynamics of prespecified epigenetic markers (WID scores) within the three surrogate tissues cervix, blood, and buccal, in order to assess whether changes are concordant or discordant, both directional and temporal (part of secondary outcome analyses)
- 2. Investigation of prespecified epigenetic markers and their correlation to non-methylation parameters, for instance whether microbiome or lung function markers are associated with any cellular/immune ageing markers (WID-RIA/WID-SOLA)
- 3. Agnostic approach, where non-methylation parameters are the outcome and predictors are defined based on DNAme to identify whether CpG sites which predict the nonmethylation features (part of subsidiary exploration).

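### Correlations of epigenetic index levels with clinical and molecular biomarkers are not committed to age adjustment, so an association can arise from shared dependence on age alone

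*SAP*

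**What the plan says.** SAP 6.4.4 first sets out mixed models for the time course of the indices; both example equations contain baseline age and a per-woman random term. It then says that this covers the dynamics, and adds a separate analysis: "it will be investigated whether epigenetic indices in certain tissues are associated with other clinical or molecular health-related biomarkers via correlation analysis". No coefficient, covariate or time point is given. The only caveat is "No causality can be established for these factors".

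Section 7 item 2 plans to correlate prespecified indices with non-methylation parameters, for instance "whether microbiome or lung function markers are associated with any cellular/immune ageing markers (WID-RIA/WID-SOLA"). Age adjustment is not mentioned there either.

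Other parts of the SAP bear on age:
- 4.1.1 admits "Women aged 30 to 60".
- 5.4.1 lists pcgtAge and a "Group of markers indicative of (stem) cellular age" among the indices.
- 6.4.1 includes, as a quality check, "we will also investigate correlation of WID general age with chronological age".
- Section 6 states "Many of the assessed factors are influenced by age", then says that "factors may be associated as covariates in mixed-effects models if necessary".
- 6.4.2 assumes a general correction of the indices for immune cell composition. It makes covariate adjustment optional when score changes are related to clinical factors.

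**The concern.** If an ageing score and a biomarker such as lung function both move with age, they will correlate across women aged 30 to 60 even when the score says nothing about lung function at a given age. The SAP recognises age dependence in general and puts baseline age into its example mixed models, but does not carry it into the correlation analysis. The general covariate rule in section 6 is optional and tied to mixed models, and a correlation is not a mixed model.

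At stake is the interpretation of the biomarker links. Sections 5.4.3 and 6.14 say that the biological meaning of epigenetic ageing signatures is unclear and look for ties to clinically meaningful features. A correlation that only reflects age would seem to supply such a tie. Disclaiming causality does not help, because the doubt is whether the association holds anything beyond age. The multiplicity corrections that 5.1 allows would not remove it either, because it is confounding and not a chance finding.

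**Working it through.** **The plan's own figure.** The SAP gives none for this analysis. Its one power statement (3.6) concerns a difference of 0.2 in an index with SD 0.44 and n = 60. As a paired comparison at two-sided 0.05 it reproduces: 0.2/0.44 × √60 − 1.96 = 1.56, and Φ(1.56) = 0.94. It does not bear on correlations.

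**Inputs from the SAP.** Age 30 to 60 (4.1.1); 60 women in the smoking sub-study and 120 in the diet sub-study (3.1), analysed separately (section 6); significance level 0.05 (5.1).

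**Assumed inputs.** Index–age correlation 0.3 to 0.8; biomarker–age correlation 0.2 to 0.5; no link between index and biomarker once age is known. Signs do not matter for the size of the effect.

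**Step 1, induced correlation.** With no link except age, r = r(index, age) × r(biomarker, age). The range is 0.3 × 0.2 = 0.06 to 0.8 × 0.5 = 0.40.

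**Step 2, chance of p<0.05.** By Fisher's transformation, z = atanh(r) × √(n − 3), and the chance is Φ(z − 1.96) + Φ(−z − 1.96). Here √57 = 7.55 and √117 = 10.82.

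| index–age r | biomarker–age r | induced r | z, n = 60 | chance, n = 60 | z, n = 120 | chance, n = 120 |
|---|---|---|---|---|---|---|
| 0.3 | 0.2 | 0.06 | 0.45 | 7.4% | 0.65 | 10.0% |
| 0.5 | 0.3 | 0.15 | 1.14 | 20.7% | 1.63 | 37.3% |
| 0.7 | 0.3 | 0.21 | 1.61 | 36.3% | 2.31 | 63.5% |
| 0.8 | 0.4 | 0.32 | 2.50 | 70.7% | 3.59 | 94.8% |
| 0.8 | 0.5 | 0.40 | 3.20 | 89.2% | 4.58 | 99.6% |

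**Step 3, check by simulation.** 2,000 runs per setting, age uniform on 30 to 60, one value per woman. Unadjusted correlation at 0.7 and 0.3 was significant in 35.1% (n = 60) and 64.5% (n = 120) of runs, in line with the table. The age-partial correlation was significant in 4.8% to 5.7% across all settings run. Simulation error is about √(0.05 × 0.95/2000) = 0.5 points, so this is the nominal 5%.

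**Step 4, correlation of changes.** With 80% of variance stable within a woman (assumed), correlating last-minus-first changes gave 4.4% to 5.8%. A fixed age effect cancels in the difference.

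**The case against.** The strongest reply is that the SAP does not prescribe an unadjusted correlation. Partial correlation is also correlation analysis, and age is handled in several places: 6.4.2 plots baseline scores against chronological age and adjusts the longitudinal plots for it, the example models in 6.4.4 include it, and the table in 6.16 lists it for the longitudinal epigenetic models. Section 7 opens with correlations of change against change, which are largely free of this confounding, and item 2 might be read in that light. The analysis is secondary, in a study that calls itself predominantly exploratory, and touches neither the primary endpoint nor the success rule.

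Much of this stands. A reader might infer that age-driven associations *will* be reported; the SAP supports only that they *can* be, because adjustment is left open. A reader might also infer that up to four visits per woman will be pooled as independent observations. No section says so, and section 6 assigns repeated measurements to mixed models, so that charge is not made.

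What does not stand is that the existing provisions settle the matter. They are optional or belong to other analyses. 6.4.4 sets its correlation apart from the dynamics, which points to levels, and item 2 of section 7 does not mention change.

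**Conclusion.** The point holds as a gap in specification: no section commits the correlation of index levels with biomarkers to age adjustment, in a population and with indices for which the SAP itself expects age dependence.

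The size depends wholly on the assumed age correlations. At the low end the false-positive rate is close to nominal (7% and 10%); at the high end a significant result is likely or almost certain (89% and 99.6%). A reader might go further and conclude that these correlations carry nothing but age. That restates the assumption of no other link and is not shown. Nor does the point extend equally to every index: 5.4.1 also lists risk and exposure scores, for which the SAP gives no age correlation. Correlations of within-woman change are largely unaffected.

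It is worth correcting because the variable needed is already available, but it does not threaten the main conclusions of the study.

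**What to change.** In 6.4.4 and section 7 item 2, state that:

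1. Associations of levels use one value per woman at a named time point, such as baseline, by partial correlation or regression adjusted for chronological age and cell composition. The age plots in 6.4.2 can show whether a linear age term is enough.
2. Associations with response use within-woman change, month 6 minus baseline, in line with the change-based correlation already in section 7.

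If item 2 of section 7 was meant to concern change only, saying so would be enough there.

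The cost is a few lines of SAP text and code, with no new data. The downside is that some raw correlations will shrink.
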